#### 3.5.2 Planned adjustment of significance level due to interim analysis

Because multiple statistical comparisons will be performed (interim analyses and final analysis), the risk of false positive (type I) error will be inflated. Therefore a group sequential  $\alpha$ -spending function shall be used, calculated using the O'Brien-Fleming method, with two-sided symmetric bounds. This gives p-values of 0.00005, 0.0039, 0.0184 and 0.0412 at the three interim analyses and the final analysis, respectively.

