## 3.5 Statistical interim analyses and stopping guidance

#### 3.5.1 Interim analyses

Three formal statistical interim analyses are planned on the primary and key secondary endpoints. These interim analyses are planned to take place when at least half the number of patients recruited for the final analysis have reached the 6 month, 12 month and 24 month post-operative time points (i.e. 50 H1 patients and 50 cementless THR patients have reached those time points, the CCS has been calculated and they have completed 2 weeks of activity monitoring).

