## **3.6** Timing of final analysis

The final analysis and preparation of the final report for the H1 Implant versus cementless THR comparison is planned to take place when all 200 patients have reached the 24 month post-operative time point and data for the primary and key secondary endpoints have been received. This is anticipated to be in June 2026.

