## 4 Statistical principles

### 4.1 P-values and confidence intervals

#### 4.1.1 Level of statistical significance

All applicable statistical tests will be either 1-sided or 2-sided depending on the outcome and will be performed using a 5% significance level.

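### The four significance levels in SAP 3.5.2 do not add up to the stated 5%, and whether they fall short of it or exceed it depends on information fractions that the SAP does not give

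*SAP*

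**What the plan says.** - **Looks.** SAP 3.5.1: "Three formal statistical interim analyses are planned on the primary and key secondary endpoints". With the final analysis there are four looks.
- **Timing.** The interims take place when "at least half the number of patients recruited for the final analysis have reached the 6 month, 12 month and 24 month" visits, which the section spells out as 50 patients per arm. The final analysis (SAP 3.6) takes place "when all 200 patients have reached the 24 month post-operative time point". No information fraction is given for any look.
- **Method.** SAP 3.5.2 calls the approach a group sequential alpha-spending function, "calculated using the O'Brien-Fleming method", "with two-sided symmetric bounds".
- **Result.** "This gives p-values of 0.00005, 0.0039, 0.0184 and 0.0412 at the three interim analyses and the final analysis, respectively".
- **Overall level.** SAP 4.1.1 says that tests, one- or two-sided depending on the outcome, "will be performed using a 5% significance level".

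**The concern.** SAP 3.5.2 presents the four levels as the output of a named method at a stated error rate, so they can be checked. They are the thresholds for the primary and key secondary tests at every look. SAP 3.5.3 says that interim statistics alone will not stop the trial, so the final level, 0.0412, matters most. If it is not what the method gives at 5%, a final p-value near the threshold would be classified wrongly. Correcting the threshold once data have been seen would be open to challenge; correcting it beforehand is not.

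**Working it through.** **Inputs.** Overall two-sided error 0.05 (4.1.1, 3.5.2); four looks (3.5.1); printed levels 0.00005, 0.0039, 0.0184, 0.0412 (3.5.2). The information fractions t are not in the SAP and are assumed below.

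**Formulas.** Classical O'Brien-Fleming bounds are z_k = C/√t_k, with C solved so that the probability of crossing ±z_k at any look is 0.05. The nominal level is 2[1 − Φ(z_k)]. Crossing probabilities come from recursive numerical integration of the joint normal distribution.

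**Step 1: the shape of the printed levels at t = 0.25, 0.5, 0.75, 1.**

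| Look | Printed p | z | z × √t |
|---|---|---|---|
| 1 | 0.00005 | 4.056 | 2.028 |
| 2 | 0.0039 | 2.886 | 2.041 |
| 3 | 0.0184 | 2.357 | 2.042 |
| Final | 0.0412 | 2.042 | 2.042 |

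Looks 2 to 4 share one constant, about 2.041, so they were evidently built on equal spacing.

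**Step 2: the error they spend under equal spacing.** The cumulative error is 0.00005, 0.0039, 0.0198 and 0.0479, a total of 4.79%. A simulation of 4 million paths gave 0.0480. Moving all printed values to the edge of their rounding gives 0.0478 to 0.0480, so rounding does not explain the gap.

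**Step 3: the levels for 5% under equal spacing.** C = 2.0243, so z = 4.049, 2.863, 2.337, 2.024 and p = 0.00005, 0.0042, 0.0194, 0.0429. The first printed level is right to its digits; the other three are not.

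**Step 4: other readings of the method.** None gives the printed set.

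| Reading (equal spacing) | Levels |
|---|---|
| O'Brien-Fleming-type spending, 0.025 per side | 0.00001, 0.0030, 0.0183, 0.0440 |
| Spending function with 1.96, used two-sided | 0.00009, 0.0055, 0.0215, 0.0411 |
| O'Brien-Fleming-type spending, one-sided 5% | 0.00009, 0.0055, 0.0219, 0.0427 |
| Classical, one-sided 5% | 0.0003, 0.0071, 0.0227, 0.0415 |
| Classical, two-sided, five looks | final 0.0413, different interim levels |

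**Step 5: the SAP's own schedule.** The third interim has 100 of 200 patients at 24 months, so t₃ is about 100/200 = 0.5, not 0.75. The fractions at the first two looks are unknown, because those patients contribute 6- and 12-month data. A range is therefore assumed.

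| Assumed t | Error spent by printed levels | Classical final level for 5% | Error spent by the Step 3 levels |
|---|---|---|---|
| 0.125/0.25/0.5/1 | 5.37% | 0.0480 | 5.61% |
| 0.2/0.35/0.5/1 | 5.28% | 0.0478 | 5.51% |
| 0.3/0.4/0.5/1 | 5.23% | 0.0476 | 5.46% |
| 0.4/0.45/0.5/1 | 5.19% | 0.0474 | 5.42% |

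On these fractions the total exceeds 5% because the printed second and third levels are too generous for looks that early. The printed final level is stricter than the method would give.

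**Step 6: the 287 minutes in 3.4.** With SD 100 and 100 per arm, the smallest significant mean is 258 + z × 100 × √(2/100) = 258 + 14.142z. At 0.0412 this is 258 + 14.142 × 2.0415 = 286.9; at 0.0429 it is 258 + 14.142 × 2.0243 = 286.6. Both round to 287. At 0.047 to 0.048 (z = 1.986 to 1.977) it is 286.1 to 286.0.

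**The case against.** **The levels are close to O'Brien-Fleming, and the source of the constant cannot be checked.** This is fair. The shape is right at looks 2 to 4, the first level is correct to its digits, and the source that the SAP cites for the method was not available. Even if those values are tabulated there, they do not give 5%.

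**The discrepancy is too small to matter.** Mostly fair. Under equal spacing, a test with 80% power at 0.0429 has 79.5% at 0.0412, and one with 70% has 69.4%. On the assumed fractions the excess error is 0.2 to 0.4 percentage points. That excess counts a crossing at any look as a positive finding, and 3.5.3 says that interim statistics alone will not stop the trial.

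**A reader might infer that the levels are simply conservative, and that printing 0.0429 cures the problem.** The SAP does not support this. The figures 4.79% and 0.0429 both need equal spacing, which the SAP never states and its schedule contradicts. On the assumed fractions, the equal-spacing replacement set would spend 5.4% to 5.6%, further from 5% than the printed set.

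**A reader might infer the opposite, that type I error is definitely inflated.** That is not supported either, because it rests on assumed fractions.

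**A reader might infer that the 287 minutes in 3.4 is wrong.** Section 3.4 states no significance level, and 0.0412 and 0.0429 both give 287.

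**A reader might infer that a primary p-value between 0.0412 and 0.0429 would be misjudged.** This is clear only for a two-sided test. The primary is a non-inferiority test (Table 1), sized in 3.3 with a one-sided z(1 − α) at 5%. The SAP does not say how two-sided levels apply to it.

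**Conclusion.** The point stands in limited form: the levels in 3.5.2 do not give the stated 5% under equal spacing or under fractions that fit the SAP's schedule. Under equal spacing the total is 4.79% and the final level should be 0.0429. With the third interim at about half the 24-month information, the total is about 5.2% to 5.4% and the classical final level is about 0.047 to 0.048. The mismatch between the printed set and the named method at equal spacing is certain. The direction and exact size of the error are not, because they depend on the unstated fractions. The consequence is small, and this is a low-priority correction. It is still worth making, because a prespecified decision threshold should follow from its stated method.

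**What to change.** In SAP 3.5.2:

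1. State the information fraction at each look and how it is defined, given that the first two interims use 6- and 12-month data.
2. Name one boundary: classical O'Brien-Fleming or an O'Brien-Fleming-type spending function.
3. State how the levels apply to the one-sided primary non-inferiority test.
4. Recompute and reprint all four levels so that the total is 5%. Use 0.00005, 0.0042, 0.0194, 0.0429 (classical) or 0.00001, 0.0030, 0.0183, 0.0440 (spending) only if equal spacing is justified.
5. Leave the 287 minutes in 3.4 as it is if the final level becomes 0.0429; otherwise recheck it.

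The cost is a few sentences and a short calculation, with no extra patients or data. It should be done before any interim results are seen.

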#### 3.5.3 Details of guidelines for stopping the trial early

Both the experimental arm (the H1 Implant) and the active comparator arm (cementless THR) are CE marked devices with proven safety and efficacy and by the time the first interim analysis is carried out,

most of the patients will have received their intervention. Therefore, the statistical results from the interim analyses alone will not be used to stop the trial early. However, if the interim analyses are cause for concern, safety information, as measured by adverse events and adverse device effects, will be closely assessed by the CRO and the sponsor to determine whether it can be justified to continue follow-up of the patients in the study.

## **3.6** Timing of final analysis

The final analysis and preparation of the final report for the H1 Implant versus cementless THR comparison is planned to take place when all 200 patients have reached the 24 month post-operative time point and data for the primary and key secondary endpoints have been received. This is anticipated to be in June 2026.

## 3.7 Timing of outcome assessments

The schedule of all of the study procedures is given in the study protocol.

## 4 Statistical principles

### 4.1 P-values and confidence intervals

#### 4.1.1 Level of statistical significance

All applicable statistical tests will be either 1-sided or 2-sided depending on the outcome and will be performed using a 5% significance level.

#### 4.1.2 Planned adjustment for multiplicity

#### 4.1.2.1 Multiple secondary endpoints

In order to control the overall Type I error related to multiple secondary endpoints, multiplicity adjustment shall be made using the multi-step, step-up Hochberg procedure for the likely-correlated secondary endpoints that will be undergoing statistical analysis (Table 1).

#### 4.1.2.2 Interim analyses

As described in Section 3.5.2, p-values will also be adjusted to allow for interim analyses.

#### 4.1.2.3 Subgroup analyses

The subgroup analyses described in Table 1 are designed to investigate the sensitivity of the conclusions drawn from the overall analysis, thereby increasing the confidence in the results obtained from the primary analysis and therefore will not be subjected to adjustment for type I error due to multiplicity concerns.

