## 2.2 Study objectives

The primary objective of this trial is to determine whether the H1 Implant is non-inferior to cementless THR in terms of CCS.

The key secondary objective is to determine whether the H1 Implant is superior compared to cementless THR in terms of physical activity and patient report outcome measures (PROMs).

Other secondary objectives are to compare the H1 Implant and cementless THR with respect to:

- Safety, through collection of all procedure and device related adverse events
- Noise generation, through patient survey.

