## 3.3 Sample size

The sample size was calculated on the basis of the research hypothesis. Using pilot data from two sources, the CCS rates for cementless THR and the H1 Implant were estimated to be 91%3\* and 92.7%, respectively. With a non-inferiority margin of 8% and setting the probability of a type I error to 5% and power to 80% and using the following formula:

$$n = \left(\frac{z_{1-\alpha} + z_{1-\beta}}{P_{H1} - P_{THR} - \delta}\right)^2 \left(P_{H1}(1 - P_{H1}) + P_{THR}(1 - P_{THR})\right)$$

where:

n = required sample size  $P_{H1}$  = probability of success for H1  $P_{THR}$  = probability of success for THR  $\alpha$  = probability of a type I error  $\beta$  = probability of a type II error  $\delta$  = non-inferiority margin

<sup>\*This CCS for the cementless total hip was calculated from the publication referenced, but excluded intra-operative ceramic liner fractures because these have been practically eliminated with modern day ceramic (BIOLOX®*delta*) and do not occur with polyethylene cups. The control in the RCT will be cementless BIOLOX®*delta*-on-BIOLOX®*delta* or cementless BIOLOX®*delta*-on-PE THRs.

z = is the cumulative distribution function of a standardised normal deviate

The required sample size is 93 per group. Allowing for drop-outs, this gives a sample size of 100 per treatment arm, therefore a total of 200 patients will be recruited to the study. Assuming the cementless THR group goes on to match this pilot data of 91% success, 90% of H1 patients would be required to demonstrate composite clinical success to be non-inferior to the THR patients, with the margin of 8%.

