#### Table 1. Summary of outcomes and analysis methods

Variable/outcome	Hypothesis	Outcome measure	Method of analysis
Primary: CCS	H1 Implant is non- inferior to THR	% patients achieving CCS	Blackwelder's non- inferiority test
Secondary: physical activity	H1 Implant is significantly better than THR	Average daily minutes of activity and mean bouted daily MVPA, minutes	Student's t-test (normal, equal variance) or Welch's t-test (normal, unequal variance) or Wilcoxon Rank-Sum (non-normal)
Secondary: physical performance assessment	H1 Implant is significantly better than THR	Number of chair stands in 30 seconds Time to perform stair climb test	
Secondary: HOS	H1 Implant is significantly better than THR	HOS Questionnaire	
Secondary: UCLA Activity Score	H1 Implant is significantly better than THR	UCLA Activity Score	
Secondary: safety	N/A	Adverse events and adverse device effects	N/A
Secondary: noise	N/A	Noise questionnaire	N/A
Adjustment for stratification	Odds ratios are equal across sites	% patients achieving CCS	Cochran-Mantel- Haenszel test followed by Woolf's heterogeneity test
Subgroup analysis: Low v High pre-op activity/physical assessment score/UCLA	N/A	Average daily CPM Mean bouted daily MVPA, minutes	Student's t-test or Welch's t-test or Wilcoxon Rank-Sum
Subgroup analysis: Low vs high "historical UCLA" score	-		
Subgroup analysis: male v female	N/A	% patients achieving CCS	Fisher's exact test
Subgroup analysis: small H1 Implants v all THRs	-		
Subgroup analysis: large H1 Implants v all THRs			
Subgroup analysis: H1 Implants v device type in the THR group			
Subgroup analysis: H1 Implants v bearing type in the THR group			

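### The CCS subgroups that compare H1 with THR are meant to raise confidence in a non-inferiority result, but Table 1 gives them only a test of equality, with no margin and no interval for the difference

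*SAP*

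**What the plan says.** The primary objective in SAP 2.2 is to "determine whether the H1 Implant is non-inferior to cementless THR in terms of CCS". Section 3.3 sets the margin at 8 percentage points, and Table 1 assigns Blackwelder's non-inferiority test.

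Section 4.1.2.3 presents the subgroup analyses as a probe of how sensitive the overall conclusions are, "thereby increasing the confidence in the results obtained from the primary analysis". It uses that purpose as the reason for making no multiplicity adjustment.

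Table 1 then lists the CCS subgroups. Four rows compare H1 with THR: small H1 devices against the whole THR arm, large H1 devices against the whole THR arm, "Subgroup analysis: H1 Implants v device type in the THR group" and "Subgroup analysis: H1 Implants v bearing type in the THR group". Their hypothesis is not applicable or blank. The method column shows "Fisher's exact test" once, in the row for sex at the top of the block. The cells beneath are empty, and a merged cell is the natural reading.

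Other relevant text:
- Section 4.1.1 sets a 5% level but leaves one- or two-sided testing to depend on the outcome.
- Section 4.1.4 makes all intervals two-sided 95%.
- Section 6.2 promises 95% intervals for categorical summaries, in a section that reports outcomes by treatment group. It does not promise one for the difference between H1 and a THR subgroup.

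**The concern.** The stated purpose and the method do not match. The conclusion under examination is that H1 is not worse than THR by more than 8 points. The null hypothesis of Fisher's test is that the two CCS proportions are equal. Failure to reject equality says nothing about whether a deficit beyond 8 points has been excluded, and the smaller the subgroup, the more often equality goes unrejected.

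The reporting of the subgroups is at stake. Readers will want to know whether the result holds against ceramic-on-ceramic and ceramic-on-polyethylene controls separately, and for small and large H1 devices. A list of non-significant p-values could be taken as reassurance when the same counts would fail the trial's own margin.

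**Working it through.** **Inputs from the SAP.** CCS of 91% for THR and 92.7% for H1, margin of 8 points, 100 patients per arm (3.3); 5% level (4.1.1); two control bearing types (3.3, footnote).

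**Assumptions.** The SAP gives no subgroup sizes, so 25, 50 and 75 THR patients of a type are set against all 100 H1 patients. With two bearing types, at least one holds no more than half of the THR arm. The test is taken as two-sided, with the one-sided version (towards H1 being worse) also shown. A deficit equal to the margin means H1 at 91 - 8 = 83%.

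**Plan's own figure.** The SAP states no power or precision for these subgroups, so there is nothing to reproduce. The printed rates in the 3.3 formula give (1.645 + 0.842)² × (0.927×0.073 + 0.91×0.09) / 0.097² = 98.3, so 99 per group against the stated 93. A THR rate of 90.6% before rounding would give 93. That is a separate matter and does not enter here.

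**Step 1: how often Fisher's test is non-significant.** For each pair of success counts (x, y), compute the Fisher p-value. Then sum Bin(x; 100, p_H1) × Bin(y; n, p_THR) over all pairs with p > 0.05.

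| THR patients (n) | H1 83%, two-sided | H1 83%, one-sided | H1 79%, two-sided | H1 92.7% (planned), two-sided |
|---|---|---|---|---|
| 25 | 90% | 85% | 79% | 96% |
| 50 | 78% | 70% | 56% | 95% |
| 75 | 71% | 63% | 44% | 95% |

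**Step 2: what a non-significant result tells the reader.** Divide its frequency at the planning rates by its frequency at the margin: 96/90 = 1.07, 95/78 = 1.22 and 95/71 = 1.34. A ratio so close to 1 is very weak evidence. A significant result in favour of H1 would be positive support, but it occurs in only 4 to 5% of trials at the planning rates.

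**Step 3: the same question with an interval.** Read the two-sided 95% lower limit against -8%. At a true 8-point deficit it clears -8% in about 2.5% of trials by construction (normal approximation). At the planning rates the Wald limit still crosses -8% in about 71%, 46% and 35% of trials with 25, 50 and 75 THR patients. With 50 patients it therefore clears in 100 - 46 = 54%, a ratio of roughly 54/2.5 = 22, against 1.22 for Fisher non-significance.

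**Step 4: an example.** Take H1 84/100 and one THR type 45/50.
- Fisher p = 0.455.
- Difference = 84.0 - 90.0 = -6.0 points.
- SE = √(0.84×0.16/100 + 0.90×0.10/50) = 5.61 points.
- Wald two-sided 95% interval: -6.0 ± 1.96×5.61 = -17.0 to +5.0. The one-sided 95% lower limit is -6.0 - 1.645×5.61 = -15.2.
- Newcombe interval: the Wilson limits are 75.58 to 89.90% (H1) and 78.64 to 95.65% (THR). The lower limit is -6.0 - √(8.42² + 5.65²) = -16.1 and the upper is -6.0 + √(5.90² + 11.36²) = +6.8.

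Fisher's test shows no significant difference, yet each of these lower limits lies well beyond -8.

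**Step 5: the H1-size rows.** Against all 100 THR patients, a true 83% v 91% is missed (two-sided) in 81% of trials with 25 H1 patients and 75% with 50. The problem is not confined to the device-type and bearing-type rows.

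**The case against.** A reader might infer that the SAP treats a non-significant subgroup result as confirmation. It does not say so. Section 4.1.2.3 speaks of investigating sensitivity, Table 1 states no subgroup hypothesis, and no rule equates p > 0.05 with support. That objection stands. What remains is that the SAP claims a gain in confidence and supplies no criterion by which these rows could deliver it.

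The miss rates also rest on assumed subgroup sizes and a two-sided test. One-sided, the range over 25 to 75 THR patients is about 85% to 63%. Even with all 100 THR patients the two-sided miss rate is 68%, so much of the effect comes from a trial not designed to detect an 8-point difference by a test of equality. This weakens any claim about subgrouping as such, but not the point that the test is wrong for the purpose.

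The assignment of Fisher's test to these rows depends on reading the table cell as merged. No other method is shown for them.

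It would also be too strong to expect an interval usually to fail. At the planning rates the two-sided limit crosses -8% in a majority of trials with 25 THR patients, but in a minority with 50 or 75.

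Finally, the trial's main claim rests on the full-arm non-inferiority test, which no subgroup result alters. That is correct and limits the consequence.

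**Conclusion.** The concern holds as a mismatch between purpose and method. A test of equality without a margin or an interval cannot increase confidence in a non-inferiority conclusion. With 100 H1 patients, 25 to 75 THR patients of a type and a two-sided 5% test, a deficit as large as the margin goes undetected in about 90% to 71% of trials, against non-significance in about 95% when H1 performs as planned. These figures depend on subgroup sizes and a choice of sidedness that the SAP does not fix, and on reading the Fisher entry as covering the rows below it. The documents do not support saying that the plan accepts non-significance as proof, or that the primary analysis is compromised. The matter is worth correcting before analysis because it governs what the report may say about the subgroups.

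**What to change.** In Table 1, for all four CCS subgroup rows that compare H1 with THR (small H1, large H1, THR device type, THR bearing type), replace Fisher's exact test with the H1-minus-THR difference in CCS and its two-sided 95% confidence interval, consistent with 4.1.4. Use a method suited to small counts, such as a Miettinen-Nurminen or Newcombe score interval: with 25 THR patients at 91%, only 25 × 0.09 = 2.25 failures are expected. Show each interval against -8%.

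In 4.1.2.3, replace the clause on increased confidence with a statement that these analyses are descriptive and that a non-significant difference is not evidence of non-inferiority.

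The change is to SAP wording only and uses the same counts. It costs slightly more reporting, and some subgroup results will look less reassuring, because the lower limit can cross -8% even when H1 performs as planned.
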